**Remarks:**

1. Events can only be combined into one and the same AE if their start and stop dates are complete.

2. In case the completely missing end date is imputed (for phase allocation), this date is also considered as a complete date.
3. Time during the day is not considered when determining overlap of events.

#### **4.1.2. Analysis of Adverse Events**

Number and percentage of subjects with at least one particular AE (unsolicited/solicited) will be tabulated. Unsolicited AEs will be summarized by System Organ Class and Preferred Term. Solicited AEs will be summarized by class (local, systemic) and preferred term.

For solicited AEs, the following tables will be provided: summary table, by worst severity grade, grade 3, related to study vaccine (systemic only). Note: for solicited AEs, duration is defined as number of days from the start of the event until resolution of the event. If the investigator reports multiple events of the same solicited AE in a reporting period (e.g., due to differences in their relationships to the study vaccine), duration will be derived from the onset date of the first event and the resolution date of the last event (date of resolution last event – date of first onset + 1). The time to first onset is defined as (date of first onset – reference date + 1). The reference date is the start date of the regimen period.

For unsolicited AEs, the following tables will be provided: summary table (including SAE, fatal outcome, discontinuation), all AEs, most frequent AEs, grade 3, permanent stop of vaccine, AE related study vaccine, SAE.

Listings and/or subject narratives will be provided as appropriate, for those subjects who die, discontinue study vaccinations due to an AE, or experience a severe AE or SAE.

#### **4.1.3. Handling of Missing Data for Adverse Events**

Missing data will not be imputed.

#### **4.1.4. Solicited Local (Injection Site) Reactions**

The analysis of local solicited adverse events will include:

- Erythema
- Induration/swelling
- Pain/tenderness

#### **4.1.5. Solicited Systemic Adverse Events**

The analysis of systemic solicited adverse events for pediatric subjects will include:

- Loss of appetite
- Vomiting
- Diarrhea
- Decreased activity/lethargy
- irritability/crying
- Fever (i.e., body temperature  $\geq 38$  °C)

## 4.2. Vital Signs and Physical Examination Findings

Heart rate, respiratory rates and oxygen saturation (SpO2) will be summarized with descriptive statistics.

Body temperature (diary and onsite measurements during first 8 days) will be tabulated by half degree increments, in each analysis period. The number and percentage of subjects with values beyond the following clinically relevant limits will be tabulated:

- Respiratory rate >45 breaths/minute
- Pulse rate >140 beats/minute
- Oxygen saturation (SpO2) <95%

A listing of a subject's narrative may be created in case a pausing rule is met. Vital signs results and abnormal physical examination findings will be included in the subject narratives. A mock layout of the subject narrative is provided in the DPS.

## 5. RSV INFECTIONS

### 5.1. Definitions

The secondary endpoint related to RSV infection:

- Severe RSV-LRTI as a preliminary indication of ERD  
Severe RSV-LRTI will be defined as the presence of severe LRTI as assessed by the CEC, and confirmation of RSV infection by nasal (mid-turbinate or nasopharyngeal) sample using independent RT-PCR by a central laboratory. If no central laboratory RT-PCR result is available, a positive test result (including commercial test results) for RSV from a local laboratory (if available) could be used to confirm RSV infection upon evaluation by the CEC.

### 5.2. Analysis of RSV infection

The number and percentage of subjects with RTI and RSV confirmed RTIs will be tabulated.

As soon as 3 or more events (regardless of group) of 'severe RSV-LRTI' have been observed, the proportions per group and the confidence limits for the difference in proportions (using Wilson score method) between the Ad26.RSV.preF group and control group (pooling placebo/placebo/Nimenrix and placebo/placebo/placebo) will be constructed. The upper (one-sided) 95% confidence limit for the difference, the lower (one-sided) 95% confidence limit for the difference and the lower (one-sided) 80% confidence limit will be constructed.

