Attachment 3: Guidance on Study Conduct during the COVID-19 Pandemic

Amendment 5 (Issued date: 05 July 2019)**The overall reason for the amendment:**

This amendment is made to align the global protocol with changes made following requests from the German Health Authority:

- Clarification is added that the consent of both parents/legal guardians will be required in countries where this is specified by local regulation;
- Clarification is added on the reporting of any RTI or case of otitis media fulfilling the criterion of an SAE: all RTIs and cases of otitis media meeting seriousness criteria will be reported as SAEs; any RTI or case of otitis media reported as an (S)AE that is found to be positive for RSV will be excluded from the analyses of (S)AEs. However, the case will remain in the clinical database and will be tabulated separately in the clinical study report;
- Update of the monitoring rule for severe RSV-LRTI to reduce the numbers of events required to start an analysis from 3 to 2.

The table below gives an overview of the rationale for each change and all affected sections

Rationale: To clarify that in countries where local regulation requires that both parents/legal guardians give consent, this will be applicable.

*4.1 Inclusion Criteria**9.1.3.1 Screening Phase: Days -42 to 1**16.1 Study-Specific Design Considerations**16.2.3 Informed Consent**16.2.4 Privacy of Personal Data*

Rationale: To clarify the reporting of any RTI or case of otitis media fulfilling the criterion of an SAE.

*Synopsis: RTI Procedures**Time and Events Schedule**9.2.2 RTI Procedures**11.6 RSV Infection**11.7 Safety Analyses**12.1.1 Adverse Event Definitions and Classifications*

Rationale: Update of the monitoring rule for severe RSV-LRTI to reduce the numbers of events required to start an analysis from 3 to 2.

*Synopsis: Statistical Methods**11.3.1.3 Monitoring Rule for Severe RSV-LRTI*

Rationale: In addition, other minor changes, clarifications, and corrections were made throughout the protocol.

Amendment 4 (Issued date: 08 April 2019)

The overall reason for the amendment: To introduce more active follow-up of ongoing RTIs/otitis media cases to capture the potential worsening of RTI/otitis media cases that are reported as not severe during the initial RTI visit and to clarify the responsibilities of the CEC in terms of evaluation of RTI cases and severity grading of RTIs.

Updates and clarifications are made as specified below.

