The number of subjects for this study will provide a preliminary safety and immunogenicity assessment. Control recipients are included for blinding and safety purposes and will provide additional control specimens for immunogenicity assays. While mild to moderate vaccine reactions (local site and systemic responses) are expected, AEs that preclude further dose administration or more serious ones that would limit product development are not anticipated.

Monitoring Rule for Severe RSV-LRTI

A monitoring rule with respect to severe RSV-LRTI will be installed for this study. If 1 event (regardless of the group) of severe RSV-LRTI is observed, no analysis will be done. If 2 or more events (regardless of the group) of severe RSV-LRTI have been observed, confidence limits for the difference in proportions (using Wilson score method) between the Ad26.RSV.preF group and control group (pooling placebo/placebo/Nimenrix and placebo/placebo/placebo) will be constructed by the external statistician who is supporting the IDMC:

- If the upper (one-sided) 95% confidence limit for the difference is $<10\%$: continue the study; if study enrollment is still ongoing, continue enrollment.
- If the upper (one-sided) 95% confidence limit is $\geq 10\%$ and the lower (one-sided) 80% confidence limit is >0 : more frequent active monitoring of subjects, including weekly calls within the RSV season and more frequent medical review will be initiated.
- If the upper (one-sided) 95% confidence limit is $\geq 10\%$ and the lower (one-sided) 95% confidence limit is >0 : halt enrollment in this study or the next study; more frequent active monitoring of subjects, including weekly calls within the RSV season and more frequent medical review for all enrolled subjects should be initiated.

For example: assuming complete enrollment, if 2 or 3 severe RSV-LRTI events are observed and all occurred in the Ad26.RSV.preF group, the lower (one-sided) 80% (but not the 95%) confidence limit will be >0 and monitoring will be increased. If 4 severe RSV-LRTI events are observed and all occurred in the Ad26.RSV.preF group, the lower (one-sided) 95% confidence limit will be >0 and enrollment in all pediatric studies with Ad26.RSV.preF will be halted and monitoring of all enrolled subjects will be increased.

The IDMC will review unblinded data and give a recommendation to the sponsor. More details on this monitoring rule are specified in the IDMC charter.

Planned Analyses

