11.3.1.3. Monitoring Rule for Severe RSV-LRTI

In this section ‘severe RSV-LRTI’ refers to the assessment made by the CEC.

With respect to the secondary endpoint ‘severe RSV-LRTI’, a monitoring rule for severe RSV-LRTI is as follows.

- If 1 event (regardless of group) of ‘severe RSV-LRTI’ is observed, no analysis will be done. *Note:* However, the IDMC will be informed and may convene.
- As soon as 2 or more events (regardless of group) of ‘severe RSV-LRTI’ have been observed, confidence limits for the difference in proportions (using Wilson score method) between the Ad26.RSV.preF group and control group (pooling placebo/placebo/Nimenrix and placebo/placebo/placebo) will be constructed by the external statistician who is supporting the IDMC:
 - If the upper (one-sided) 95% confidence limit for the difference is $<10\%$: continue the study; if study enrollment is still ongoing, continue enrollment.
 - If the upper (one-sided) 95% confidence limit is $\geq 10\%$ and the lower (one-sided) 80% confidence limit is >0 : more frequent active monitoring of subjects, including weekly calls within the RSV season and more frequent medical review will be initiated.
 - If the upper (one-sided) 95% confidence limit is $\geq 10\%$ and the lower (one-sided) 95% confidence limit is >0 : halt enrollment in this study or the next study; more frequent active monitoring of subjects, including weekly calls within the RSV season and more frequent medical review for all enrolled subjects should be initiated.

For example: assuming complete enrollment, if 2 or 3 severe RSV-LRTI events are observed and all occurred in the Ad26.RSV.preF group, the lower (one-sided) 80% (but not the 95%)

confidence limit will be >0 and monitoring will be increased. If 4 severe RSV-LRTI events are observed and all occurred in the Ad26.RSV.preF group, the lower (one-sided) 95% confidence limit will be >0 and enrollment in all pediatric studies with Ad26.RSV.preF will be halted and monitoring of all enrolled subjects will be increased.

More details on this monitoring rule are specified in the IDMC charter.

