11.9.2. Independent Data Monitoring Committee (IDMC)

An IDMC will be established to review safety data, and as needed on an ad hoc basis to ensure the continuing safety of the subjects enrolled in this study. The IDMC will convene to discuss any situation that meets a study vaccination pausing rule (see Section 11.10).

The presence of severe LRTI and the occurrence of RSV infection will be determined by the CEC, a separate committee (see Section 11.9.1).

The IDMC will monitor severe RSV-LRTI as assessed by the CEC according to the rule described in Section 11.3.1.3 and further detailed in the IDMC charter.

The IDMC will consist of members independent of the sponsor, including at least one medical expert in the relevant therapeutic area and at least one statistician. An immunologist may be included on an ad hoc basis, as needed. The IDMC responsibilities, authorities, and procedures will be documented in its charter. An external statistician independent of the sponsor and not involved in the interim, primary, and final analyses of the study will prepare the data and perform all analyses for review by the IDMC.

In any case(s) under review, the IDMC will review unblinded data.

Details on the intervals of the safety evaluations will be provided in the IDMC charter.

Safety data from the interim and primary analyses will be shared with the IDMC.

If any question arises related to safety, the IDMC will be convened.

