## 1. INTRODUCTION

An independent data monitoring committee (IDMC) will be established in the study VAC18194RSV2002 to review safety data and to ensure the continuing safety of the subjects enrolled in this study.

This statistical analysis plan (SAP) contains the derivations and statistical methods for the analysis to be conducted for the IDMC. There is one planned IDMC analysis in the current study, to be performed on Day 8, after the first dose in the first 12 toddlers (6 receiving the active vaccine and 6 receiving placebo). Snapshot data will be used—The database will be cleaned on an ongoing basis, there will be no formal data cleaning for the IDMC analyses.

The IDMC will review unblinded data. An external statistician (the statistical support group (SSG) statistician) independent of the sponsor and not involved in the interim, primary, and final analyses of the study will prepare the data and perform all analyses for review by the IDMC .

Details on each table, graph and listing to be generated for the IDMC is described in a separate data presentation specifications (DPS) document. However, the study team or IDMC may request additional deliverables, with this SAP serving as a guidance. Safety data from the interim (if applicable), primary and final analyses will also be shared with the IDMC.

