### 1.2. Trial Design

This is a multi-center, randomized, observer-blind, Phase 1/2a study, to be conducted in 48 male and female RSV-seronegative toddlers aged  $\geq 12$  to  $\leq 24$  months.

Each subject's RSV serostatus will be assessed by RSV enzyme immunoassay (EIA) at screeninga. *Note:* serostatus may be assessed via this assay if available from a different study of the sponsor (VAC18194RSV2001). If done within 42 days of first dose, this assessment would not have to be repeated in the absence of a history of respiratory infection during that period. Additionally, the seronegative status will be confirmed by the absence of an anamnestic humoral immune response (which is usually observed 7-10 days post antigen re-exposure in RSV seropositive subjects) from blood samples taken on Day 8 after the first dose.

---

a The cut-off for seronegativity is a titer  $<1$  EIA unit.

Subjects will be randomized 1:1 to receive either Ad26/Ad26/Ad26 (at  $2.5 \times 10^{10}$  vp) or placebo/placebo/Nimenrix®a,b (or placebo/placebo/placebo) (Table 1).

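### SAP 5.2 builds the severe RSV-LRTI limits only from 3 events, but the current protocol requires them from 2, so the SAP gives no limits for the 2/0 outcome on which the protocol acts

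*SAP*

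**What the plan says.** The SAP is the plan for the IDMC outputs: it "contains the derivations and statistical methods for the analysis to be conducted for the IDMC". Its Section 5.2 constructs the two one-sided 95% limits and the lower one-sided 80% limit for the difference in proportions "As soon as 3 or more events (regardless of group"). No other SAP text covers two events.

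The current protocol sets a lower trigger in two places. Section 11.3.1.3 says "As soon as 2 or more events (regardless of group"), and the Synopsis (Statistical Methods) says "If 2 or more events (regardless of the group) of severe RSV-LRTI have been observed". The example in Section 11.3.1.3 covers the case "if 2 or 3 severe RSV-LRTI events are observed and all occurred in the Ad26.RSV.preF group" and places it in the increased-monitoring tier. Section 11.9.2 ties the IDMC to this rule: "The IDMC will monitor severe RSV-LRTI as assessed by the CEC according to the rule described in Section 11.3.1.3".

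As background only, the log for Amendment 5 records an intention to "reduce the numbers of events required to start an analysis from 3 to 2". The lower trigger was therefore a deliberate change.

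The SAP also describes a trial "to be conducted in 48 male and female RSV-seronegative toddlers" (24 per group). Protocol Section 3.1 now has 36 (18 per group) and notes 37 enrolled at Amendment 6.

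**The concern.** The rule watches for severe RSV-LRTI as a preliminary sign of enhanced respiratory disease in seronegative toddlers. The protocol gives the construction of the limits to the external statistician who supports the IDMC, and the SAP is that statistician's plan. Both documents use the same interval method, the same pooled control group and the same three limits. They differ only in the event count that starts the calculation.

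If the SAP is followed as written, the limits are not produced at two events. What is at stake is the early-warning tier at 2/0, not the halt tier.

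**Working it through.** **Inputs.** From protocol 11.3.1.3: Wilson score limits for the difference, Ad26.RSV.preF minus control. The tiers are:
- continue if the upper 95% limit is below 10%;
- increased monitoring if the upper 95% limit is at least 10% and the lower 80% limit is above 0;
- halt if the upper 95% limit is at least 10% and the lower 95% limit is above 0.

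All limits are one-sided. Group size is 18 (protocol 3.1). The control rate of 1% and vaccine-group rate of 25% come from protocol 11.2. Vaccine-group rates of 5% and 10% are assumptions.

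**Formulas.** For x events in n, the Wilson limits are

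l, u = [2x + z² ∓ z√(z² + 4x(1 − x/n))] / [2(n + z²)].

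With d = p1 − p2, the limits for the difference (Newcombe's method, the SAP's reference 2, without continuity correction) are

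L = d − √[(p1 − l1)² + (u2 − p2)²] and U = d + √[(u1 − p1)² + (p2 − l2)²].

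**Reproducing the protocol's 2/0 example at 18/18.** Here d = 2/18 = 0.1111.

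- z = 1.645: for 2/18, l1 = (6.706 − 5.154)/41.411 = 0.0375 and u1 = (6.706 + 5.154)/41.411 = 0.2864. For 0/18, l2 = 0 and u2 = 2.706/20.706 = 0.1307.
  - Lower 95%: 0.1111 − √(0.0736² + 0.1307²) = 0.1111 − 0.1500 = **−3.9%**
  - Upper 95%: 0.1111 + 0.1753 = **28.6%**
- z = 0.842: l1 = 0.0629 and u2 = 0.0379.
  - Lower 80%: 0.1111 − √(0.0482² + 0.0379²) = 0.1111 − 0.0613 = **+5.0%**

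This is increased monitoring, as the protocol's example says.

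**Sensitivity of the 2/0 result.** 19/18 and 18/19 allow for 37 enrolled; 24/24 is the SAP's size.

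| Groups | Lower 80%, uncorrected | Lower 80%, continuity-corrected |
|---|---|---|
| 18/18 | +5.0% | +0.4% |
| 19/18 | +4.6% | +0.1% |
| 18/19 | +5.1% | +0.8% (0.0075 before rounding) |
| 24/24 | +3.7% | +0.3% |

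In all eight cases the lower 95% limit is below 0 and the upper 95% limit is above 10%, so the tier is the same.

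**Other two-event outcomes (18/18, uncorrected).** 1/1 has upper 95% 16.5% and lower 80% −7.2%, so it meets no tier. 0/2 has upper 95% 3.9%, so it means continue. Only 2/0 leads to action.

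**Effect of the trigger.** Tiers were summed over all binomial outcomes at 18/18, control rate 1%, uncorrected, on final counts. Because 2/0 is the only actionable two-event outcome, the difference between triggers equals P(2/0). At 25% this is 153 × 0.25² × 0.75¹⁶ × 0.99¹⁸ = 8.0%.

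| Vaccine-group rate | P(increased monitoring or halt), trigger 2 | Same, trigger 3 | P(2/0) |
|---|---|---|---|
| 25% (protocol) | 94.2% | 86.2% | 8.0% |
| 10% (assumed) | 50.0% | 26.4% | 23.7% |
| 5% (assumed) | 19.8% | 5.7% | 14.1% |

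If the rule is applied after each event, in random order and with full-enrolment denominators, the figures are 94.8% v 86.3%, 51.7% v 26.5% and 20.7% v 5.8%. The probability of a halt at 25% v 1% is the same under both triggers: 79.7% on final counts and 81.9% sequentially. With continuity correction on final counts at 25%, the comparison is 91.3% v 83.3%, with a halt probability of 62.3% under both.

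**A limit on the reproduction.** The protocol's example reproduces only in part by this method. At 18/18 uncorrected, 3/0 has a lower 95% limit of +0.3%, which is a halt, whereas the example places 3/0 in increased monitoring. The 79.7% counts 3/0 as a halt. This leaves the 2/0 result unchanged.

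**The case against.** The strongest reply is that the safeguard does not rest on the SAP. The protocol itself tells the external statistician to build the limits at two events and binds the IDMC to that rule. Section 11.3.1.3 has the IDMC informed at the first event, Section 11.9.1 has each severe case confirmed by the CEC passed on to the IDMC, and the IDMC sees unblinded data. SAP Section 1 plans only one IDMC analysis (Day 8 after the first dose, first 12 toddlers), describes itself as guidance, and allows extra outputs on request. It does not state the action tiers. The IDMC charter, which holds more detail on the rule, is not among the documents and may already carry the right trigger.

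All of this stands as mitigation. It makes a missed 2/0 less likely, and it means the probabilities above describe the case in which nobody applies the protocol at two events. It does not remove the conflict. Section 5.2 goes beyond the Day 8 analysis to state a trigger for this rule, and that trigger differs from the protocol's. The SAP's provision for additional deliverables works only if someone notices the gap and asks.

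**Conclusion.** The concern holds. SAP 5.2 and the current protocol give different triggers for the same safety rule, and the difference falls on 2/0, the one two-event outcome that calls for action. That result does not depend on continuity correction or on which of the documents' sample sizes is used.

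If the SAP alone governed, the chance of reaching increased monitoring or a halt would drop by 8.0 percentage points at the protocol's 25% v 1%, and by 23.7 and 14.1 points at the assumed rates of 10% and 5% (18/18, uncorrected, final counts). The halt tier is unaffected, and outcomes with three or more events, such as 4/1, are still analysed.

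The mismatch between the two texts is certain. Whether it would change conduct depends on the charter and on which document the statistician follows. It should be corrected because it is a wrong decision threshold in the IDMC statistician's own plan. The figure of 48 toddlers is outdated text that does not alter the 2/0 result and would not be a material point alone.

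**What to change.** Amend SAP Section 5.2 so that its event trigger is the one in current protocol Section 11.3.1.3, preferably by direct reference to that section so that the two cannot diverge again. Confirm that the IDMC charter states the same trigger. In the same amendment, update the sample size in SAP Section 1.2 and Table 1 to the current protocol, with the note that 37 were enrolled at Amendment 6.

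The cost is a short SAP amendment and a charter check, plus one small computation if two events occur. No new clinical rule is involved.
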